#### 4.4. Study Arms

#### 4.4.1 Attention control

These patients will be instructed via text message and email to fast at least 16 hours per day every day. For the next 16 weeks, they will receive a daily text message via the Way to Health

platform asking if they fasted for at least 16 hours over the past 24 hours. If they fail to respond, reminder text messages will be sent. Once per week, they will receive a text message asking them to weigh themselves and check their blood pressure, and reply with the results via text message

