# 3. Study Design

#### 3.1. General Overview

The IFAST study is a two-arm randomized controlled trial aimed at evaluating whether a soft commitment device increases uptake and adherence to an intermittent fasting dietary pattern compared with control in patients with hypertension and obesity. The study will randomize 34 patients with hypertension and obesity to a 12-week intervention employing a commitment pledge, involvement of a supportive partner, setting of implementation intentions, and multiple daily reminder text messages or to an attention control involving daily text messages alone.

Following the intervention, there will be a 6-week follow-up period (see study protocol figure below).

The study will be conducted using Way to Health, a research information technology platform at the University of Pennsylvania used previously for behavioral interventions.

After institutional review board (IRB) approval of the study, patients who meet the eligibility criteria will be approached in select cardiology clinics and invited to participate. Those who qualify and express interest will provide informed consent to the study procedures via the Way to Health platform. All patients will receive a blood pressure cuff and scale, which will be used to measure blood pressure and weight weekly. Within the Way to Health platform, patients will be randomized to the intervention or control arms. All other management decisions are completely at the discretion of the care providers. Data capture will include:

- **Baseline case report form** (for each patient) collecting clinical information abstracted from the medical record
- **Baseline survey** collected via the Way to Health platform including psychometric questions, dietary patterns, and experiences with weight loss and dieting
- Daily adherence to an intermittent fasting dietary pattern collected via self-report from text messages
- Weekly weight and blood pressure measurement collected via self-report from text messages

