#### 3.3.2. Exclusion Criteria

Patients are excluded if they meet any of the following criteria:

- 1. Unable or unwilling to provide informed consent, including but not limited to cognitive or language barriers (reading or comprehension)
- 2. Type 1 diabetes
- 3. Use of insulin or insulin secretagogues (sulfonylureas, metaglinides)
- 4. Use of medications that require food intake
- 5. Ongoing use of pharmacologic therapy for weight loss
- 6. Self-reported eating disorder
- 7. Other medical condition that could be harmed by intermittent fasting as judged by study physician
- 8. Anticipated life expectancy less than 6 months
- 9. Any other reason why it is not feasible to complete the entire 6-month study

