#### 4.4.1. Soft commitment device

Patients randomized to the commitment device arm will be asked to visit the Way to Health platform. There, they will identify a support person, a family or friend who they speak to frequently and who is invested in their health. They will then complete a series of questions intended to create implementation intentions. Specifically, they will pick a time for their fast to begin each 24-hour period and a time for their fast to end. They will also develop strategies to deal with hunger arising during a fast period. After this process, they will sign a contract pledging to adhere to the 16:8 time-restricted feeding dietary pattern, and acknowledging that their support person will receive a copy of the contract and weekly updates about their adherence to the regimen.

For the next 12 weeks, participants in this arm will receive reminder text messages two times daily via Way to Health: Once at the start of their fast period and once during the meal that they skip during the fast period. Each week, participants and their support partner will also receive a text message noting how many days in the previous week they successfully fasted for at least 16 hours. After the 12 week intervention, these text messages will stop, but for the entire 18-week period, participants in this arm will receive the same text messages as the attention control arm: A daily text message asking if they fasted for at least 16 hours over the previous 24 hours, and a weekly text message asking for weight and blood pressure results.

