#### 4.5. End-of-Study Questionnaire Completion

At the end of the 16-week study period, patients will be alerted by the Way to Health platform to return to the website to complete an end-of-study questionnaire regarding their experience with IF.

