#### 5. Statistical Methods

# 5.1 Primary and secondary outcome measures

The study's primary outcome measure is adherence to the IF regimen, captured via daily text message, over 18 weeks, expressed in days per week.

Secondary outcome measures will include:

- 1) Adherence to the IF regimen over 12 weeks
- 2) Change in systolic blood pressure from baseline to 12 weeks and 18 weeks
- 3) Change in weight from baseline to 12 weeks and 18 weeks

Exploratory analyses will compare change in blood pressure and weight in patients that were adherent to IF  $\geq$  4 days per week vs.  $\leq$  4 days per week

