#### 5.2. Sample Size

With 34 patients (17 per arm), we will have 90% power to detect a 1 day per week difference in adherence to IF, assuming a standard deviation in days fasted per week < 1.24 The study will

have  $\sim 50\%$  power to detect a 10 mmHg change in systolic and diastolic blood pressure (assuming a standard deviation of 15 mmHg) and a 3 kg weight loss (assuming a standard deviation of 5 kg).

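### The control arm's daily fasting query is set at 16 weeks, but the commitment arm's query and the primary outcome both run 18 weeks

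*Combined protocol and SAP*

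**What the plan says.** The documents give four different lengths for overlapping things.

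- **Control arm query (Section 4.4.1, Attention control):** "For the next 16 weeks, they will receive a daily text message via the Way to Health" platform, asking whether the patient fasted. The weekly weight and blood pressure text has no separate duration.
- **Commitment arm query (Section 4.4.1, Soft commitment device):** "for the entire 18-week period, participants in this arm will receive the same text messages as the attention control arm".
- **Primary outcome (Section 5.1):** adherence "captured via daily text message, over 18 weeks, expressed in days per week".
- **Overall design (Section 3.1):** "patients with hypertension and obesity to a 12-week intervention employing a commitment pledge", and then "Following the intervention, there will be a 6-week follow-up period", so 12 + 6 = 18 weeks.
- **Questionnaire timing (Section 4.5):** "At the end of the 16-week study period, patients will be alerted by the Way to Health platform".
- **Exclusion criterion 9 (Section 3.3.2):** "Any other reason why it is not feasible to complete the entire 6-month study".

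Section 5.3 scores any day without reported adherence as non-adherent in the main analysis and compares the arms by t test. It does not say whether a day with no query counts as such a day, or what number of weeks each patient's total is divided by.

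**The concern.** The daily text is the only instrument for the primary outcome, and the Attention control section is the only place that sets how long controls receive it. A platform built from each arm's own section would stop asking controls two weeks before the commitment arm. Those self-reports could not be recovered reliably later, and the loss would fall on one arm only.

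The analysis section does not protect against this. Depending on a rule the plan leaves unstated, the same gap could inflate the apparent benefit of the intervention or hide a real one, so it cannot be assumed conservative.

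**Working it through.** **Inputs from the documents.** Query duration 16 weeks (control) and 18 weeks (commitment), Section 4.4.1. Outcome window 18 weeks, Section 5.1. 17 per arm and a 1 day/week target, Section 5.2. The SD is printed as "assuming a standard deviation in days fasted per week < 1.24 The study will", which may be 1.24, or 1 followed by citation number 24 (a pilot of 8-hour time-restricted feeding). Both values are used.

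**Assumptions.** Two-sided 5% test. The control mean μ is not in the documents, so a range is shown. f is control adherence in weeks 17–18 divided by the control arm's 18-week mean.

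**Step 1: durations.** 12 + 6 = 18 weeks, which agrees with Section 5.1 and not with 16. Queried days are 18 × 7 = 126 against 16 × 7 = 112. The shortfall is 14 days, and 14/126 = 11.1%.

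**Step 2: test.** Rejection probabilities come from the noncentral t with 32 df and noncentrality = difference / (pooled SD × √(2/17)). With equal windows and a true difference of 1.00, power is 63% at SD 1.24 and 81% at SD 1.0. Section 5.2 states 90%. That gap is a separate matter and this point does not depend on it.

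**Step 3: scenario A, 18-week denominator with unqueried days scored 0.** Shift in favour of the intervention = μ × f × 2/18, and the control SD is multiplied by (1 − f × 2/18).

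Example with μ = 4, f = 1, SD 1.24:
- Shift = 4 × 2/18 = 0.44.
- Control SD = 1.24 × 16/18 = 1.102, and pooled SD = √((1.24² + 1.102²)/2) = 1.173.
- Noncentrality = 0.444/(1.173 × 0.343) = 1.10, so the false-positive rate is 18.8%.

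| μ (days/week) | f | Shift | False positive, SD 1.24 | False positive, SD 1.0 |
|---|---|---|---|---|
| 1 | 1 | 0.11 | 6% | 6% |
| 3 | 1 | 0.33 | 13% | 17% |
| 4 | 1 | 0.44 | 19% | 26% |
| 5 | 1 | 0.56 | 27% | 38% |
| 4 | 0.5 | 0.22 | 8% | 10% |
| 4 | 0.25 | 0.11 | 6% | 6% |

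**Step 4: scenario B, each arm averaged over its own queried weeks.** The control 16-week mean is μ(18 − 2f)/16, so the shift (commitment minus control) is −μ(1 − f)/8. The control SD is multiplied by (18 − 2f)/16. At μ = 4:
- f = 1: no shift.
- f = 0.5: −0.25.
- f = 0.25: −0.38.
- f = 1.25: +0.13.

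At f = 0.5 the control mean becomes 4 × 17/16 = 4.25. A true difference of 1.00 is then measured as 5.00 − 4.25 = 0.75. Power falls from 63% to 38% (SD 1.24) or from 81% to 54% (SD 1.0). Without the SD scaling the figures are 40% and 56%.

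**Step 5: scenario C, both arms stop at week 16 but totals are divided by 18.** With no true difference the false-positive rate stays at 5%. With flat adherence, a true 1.00 is measured as 1.00 × 16/18 = 0.89. The serious problem is therefore a stop in one arm only.

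**The case against.** The strongest reply is that 16 is a leftover number and nobody would run the trial that way. The commitment arm is to get the same messages as controls for 18 weeks, which makes no sense if controls have none in weeks 17–18. Section 5.1 sets 18 weeks without distinguishing arms, and 12 + 6 gives 18. Section 4.5 applies its 16 weeks to all patients, which suggests old wording common to both arms and hence the mild scenario C.

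Scenario A also needs a second unlikely step. The Section 5.3 rule most naturally covers patients who were asked and did not answer. The larger rates further need flat adherence at a fairly high mean, and the documents give neither a control mean nor a trajectory.

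Much of this stands. A slip is the likelier reading, every bias figure is conditional, and the upper values are high-end illustrations. The objection does not remove the conflict. Messages could be identical at either length, and Section 4.5 gives 16 a second appearance. The natural reading of Section 5.3 leads to scenario B, which still compares unequal windows. Section 3.1 refers to a study figure that was not available for this review. It may show the intended timeline, but it would not remove the contradiction in the text.

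**Conclusion.** The inconsistency is real and should be corrected before the plan is relied on. As written, the arms have different observation windows for the primary outcome, with a control shortfall of 14 of 126 days.

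Whether this biases the result depends on implementation. If 16 is only a slip, there is no bias. If controls alone stop at week 16, the false-positive rate under scenario A runs from about 6% to 38% over the assumed control means of 1 to 5 days/week and the two SDs. Under scenario B, a late decline in control adherence to half its mean of 4 costs 0.25 days/week of a 1-day effect. The sign depends on a denominator rule that Section 5.3 does not give.

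Confidence is high that the passages conflict. The size of any bias rests on control means and late-adherence patterns that are assumptions. The 16-week and 6-month study lengths in Sections 4.5 and 3.3.2 need tidying, but a week-16 questionnaire would not by itself harm the primary outcome.

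**What to change.** 1. In Section 4.4.1 (Attention control), set the daily query to 18 weeks, and give the weekly weight and blood pressure text the same stated duration, since the secondary outcomes also need week-18 values.
2. In Section 5.3, state that the non-adherent rule applies only to days on which a query was sent, and that both arms use the same window and the same denominator.
3. Reconcile the study lengths in Sections 4.5 and 3.3.2 with the 12 + 6 weeks in Section 3.1.
4. If any controls have already been queried for only 16 weeks, compare weeks 1–16 in both arms, and record that change before the data are compared by arm.

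The cost is wording in four places and, if the platform does stop at week 16 for controls, at most two more weeks of automated texts for those affected. No extra patients or visits are needed. The fallback in item 4 shortens the primary window by two weeks.

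### Section 4.4 describes a non-response reminder for the daily fasting text but none for the weekly weight and blood pressure text, the only stated source of follow-up data for those secondary outcomes

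*Combined protocol and SAP*

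**What the plan says.** Section 4.4.1 (Attention control) sets out the contact rules in order. First comes the daily question about fasting. Next comes the rule for silence and, directly after it, a separate weekly request: "If they fail to respond, reminder text messages will be sent. Once per week, they will receive a text message". The request itself reads: "Once per week, they will receive a text message asking them to weigh themselves and check their blood pressure". The section ends without a reminder for that weekly request.

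Section 4.4.1 (Soft commitment device) says that "participants in this arm will receive the same text messages as the attention control arm", and lists the daily question and "a weekly text message asking for weight and blood pressure results". It mentions no reminder for either.

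Section 3.1 lists the data to be captured, including "Weekly weight and blood pressure measurement collected via self-report from text messages". No follow-up visit or other measurement of blood pressure or weight is described.

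The secondary outcomes in section 5.1 include "Change in systolic blood pressure from baseline to 12 weeks and 18 weeks" and "Change in weight from baseline to 12 weeks and 18 weeks". Section 5.3 analyses them with mixed effects regression. Its one rule for missing data scores unreported fasting days as non-adherent; it gives no rule for missing weight or blood pressure readings.

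**The concern.** The plan has two parallel text streams and writes a non-response rule for only one. The stream without a rule is the more exposed:

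- Over 18 weeks the daily question has up to 18 × 7 = 126 occasions per patient, a reminder, and a scoring rule for silence.
- The weekly request has at most 18 occasions, no described reminder and no rule for missing values. It also asks more of the patient: weigh, measure blood pressure, then reply with the results.

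The second study objective, the effect on blood pressure and weight, rests on these readings. The trial has 17 patients per arm and a stated power of only about 50% for these outcomes, so it has little room to lose values at the two weeks named in section 5.1. A reading that was never taken cannot be recovered at the analysis stage. For a patient who has stopped replying, a mixed model infers the later values under a missing-at-random assumption.

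**Working it through.** **Inputs.** Section 5.2 gives 17 per arm, a 10 mmHg systolic difference with SD 15 mmHg, and a 3 kg weight difference with SD 5 kg. It states about 50% power for both. Alpha and sidedness are not stated; I assume two-sided 5%. The documents give no response rate for the weekly text and no dropout allowance, so the reduced sample sizes below are assumptions.

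**Step 1: reproduce the plan's figure.** The standardised distance is δ = Δ / (SD × √(2/n)). For systolic pressure at n = 17, δ = 10 / (15 × √(2/17)) = 10 / (15 × 0.343) = 1.94. The normal approximation gives Φ(1.94 − 1.96) ≈ 49%, which matches the stated figure of about 50%. The noncentral t distribution with 32 degrees of freedom gives 47%. For weight, δ = 3 / (5 × 0.343) = 1.75, giving 42% (normal) or 40% (t). The stated 50% for weight is therefore not reproduced under this assumption, which is a separate matter from this point.

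**Step 2: illustrate a loss of values at a named week.** Suppose some patients in each arm give no reading at that week and only observed values are compared by t test. The same formula with smaller n, and a 95% confidence half-width of t(0.975, 2n − 2) × 15 × √(2/n), gives:

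| Per arm with a value | Assumed silent | δ (systolic) | Systolic power | Weight power | Systolic 95% CI half-width |
|---|---|---|---|---|---|
| 17 | 0 | 1.94 | 47% | 40% | 10.5 mmHg |
| 14 | 3/17 = 18% | 1.76 | 40% | 33% | 11.7 mmHg |
| 12 | 5/17 = 29% | 1.63 | 35% | 29% | 12.7 mmHg |

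**Step 3: set this against the planned analysis.** For a given rate of silence this is an upper bound on the loss. Section 5.3 fits mixed models to repeated readings, so a patient who misses week 12 but replies in the weeks on either side still contributes. The protection is weaker at week 18, which has no later reading, and weakest for a patient who stops replying early. How much is kept cannot be computed without a response rate and the correlation between weekly readings, and the documents give neither.

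**Step 4: check that a week-18 prompt exists in both arms.** Section 4.4.1 (Attention control) gives 16 weeks of texting, and section 4.5 refers to a study period of 16 weeks. Section 4.4.1 (Soft commitment device) gives 18 weeks, section 3.1 gives 12 weeks plus 6 weeks of follow-up (12 + 6 = 18), and section 5.1 places outcomes at week 18. If control texting ends at week 16, no reminder can recover a control-arm value at week 18.

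**The case against.** The strongest reply is that the plan is silent on weekly reminders and does not exclude them. That is correct. The absence is read from the order of the sentences. The device-arm section is weak corroboration, because it also omits the daily reminder that the control-arm section describes. Section 4.4 is not a full message specification either: section 6.6.1 adds weekly texts about hospitalizations, emergency visits and, for patients with diabetes, hypoglycemia, none of which appear in 4.4. The platform may in practice send weekly reminders. Even so, someone setting up the platform from section 4.4 would configure a reminder for the daily text only, and the remedy is the same in either case.

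A second reply is that reminders may achieve little, since patients who have stopped replying already receive the daily texts and their reminders. This also stands: no recovery rate can be claimed. It limits the expected benefit but is no reason to forgo a step that costs almost nothing.

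A reader might infer two stronger things that the documents do not support:

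- **That each outcome hangs on one text at week 12 and one at week 18.** It does not. Readings are requested every week and analysed by mixed models.
- **That the treatment comparison is shown to be biased.** The weekly request is the same in both arms. Response could differ, because only the device arm has partner updates and extra reminder texts, and patients who stop fasting may reply less. The documents give no response rate by arm and no link between replying and blood pressure or weight, so neither the size nor the direction of a bias can be derived.

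**Conclusion.** The point holds as a low-cost improvement to the secondary outcomes. As written, the plan attaches its non-response reminder to the daily fasting question and describes none for the weekly request that supplies all follow-up blood pressure and weight data. The consequence is mainly lost precision. Its actual size is unknown. The illustration puts the loss of systolic power at no more than 7 percentage points (47% to 40%) if 3 of 17 patients per arm have no value, and 12 points (47% to 35%) if 5 of 17 have none. These figures assume equal silence in both arms, values missing at random, a two-sided 5% test and the plan's own effect and SD. Reminders would recover only part of such a loss. The primary adherence outcome is not affected.

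**What to change.** First reconcile the 16-week control texting and study period (sections 4.4.1, Attention control, and 4.5) with the 18-week follow-up (sections 3.1, 4.4.1, Soft commitment device, and 5.1), so that a week-18 prompt exists in both arms.

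Then state in section 4.4, for both arms, that the automated non-response reminder used for the daily text also applies to the weekly weight and blood pressure text, that it is repeated over several days at weeks 12 and 18, and that values received within that week are accepted for that week. If the platform already does this, the same text records it.

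The cost is a short protocol addition and a platform setting, with no added staff. The downside is a few extra automated texts to patients who have not replied. The change has to be in place before follow-up, because later analysis cannot supply readings that were never collected.

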#### 4.3. Randomization

Once patients have received their scale and blood pressure cuff, they will be prompted by automated text message from the Way to Health platform to obtain a baseline weight and blood pressure. Once they provide baseline measurements and baseline questionnaires have been completed, they will be randomly assigned via the Way to Health platform to attention control or the soft commitment device using 1:1 allocation. Randomization will be stratified based on BMI ( $\leq$  and > 40 kg/m^2) and systolic blood pressure ( $\leq$  and > 160 mmHg) and will use blocks of 6 to ensure equal allocation over time.

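### No measurement conditions are set for home weight and blood pressure, so fed or fasted state can mix with change from baseline, mainly in within-arm change and the comparison by fasting days

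*Combined protocol and SAP*

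**What the plan says.** Participants receive a cuff and scale by post. Under section 4.3 they are "prompted by automated text message from the Way to Health platform to obtain a baseline weight and blood pressure", and they are randomised once these values and the questionnaires are in. The arm-specific instruction to fast 16 hours a day comes after assignment (section 4.4.1, Attention control).

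During follow-up the control arm gets a weekly text "asking them to weigh themselves and check their blood pressure, and reply with the results via text message". The section on the commitment device gives that arm the same weekly request. Only that arm chooses fixed fast start and end times, and it gets two daily reminders: "Once at the start of their fast period and once during the meal that they skip during the fast period".

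Section 5.1 lists "Change in systolic blood pressure from baseline to 12 weeks and 18 weeks" as a secondary outcome, and the same for weight. It also plans an exploratory comparison of BP and weight change by fasting days per week. Section 5.3 analyses both with mixed effects regression and does not say which weekly values enter. Section 5.2 gives about 50% power for 10 mmHg, "assuming a standard deviation of 15 mmHg", and for 3 kg with an SD of 5 kg. Section 6.6.1 confirms that both arms are told to fast.

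No section states time of day, time since eating, rest, posture, clothing or number of readings, at baseline or later.

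**The concern.** In most trials, loose home-measurement conditions only add noise. Here the behaviour under test, time since last eating, is also a condition of measurement. The baseline is taken before participants are told to fast. Later readings may fall many hours into a fast. A lighter scale reading on an empty stomach, or an acute effect of fasting on BP, could then be recorded as change from baseline although nothing lasting has changed. Time since the last meal is not recorded, so the analysis could neither detect nor adjust for this.

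Precision is also at stake. The baseline prompt is not repeated, and its value enters every change score for that participant. Section 5.2 already accepts only about 50% power for BP. BP and weight are the second of the two objectives in section 2, so these outcomes will be interpreted whatever their power.

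**Working it through.** **Inputs from the documents.** 17 per arm; 10 mmHg with SD 15 mmHg; 3 kg with SD 5 kg; a design difference of 1 fasting day per week (all section 5.2).

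**Assumptions (not in the documents).** Two-sided 5% level. The 15 mmHg and 5 kg are SDs of a change between single readings; section 5.2 does not say. Fed-fasted weight gap 0.5-1.5 kg. Fed-fasted BP shift 1-5 mmHg, direction left open. Within-person SD of a single systolic reading 4-10 mmHg, and of a single weight 0.5-1.5 kg.

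**1. The plan's own figures.** For BP, the standardised difference is 10 / (15 × √(2/17)) = 1.94. Power is 49.3% by the normal approximation and 47.0% by the noncentral t, so the stated figure of about 50% reproduces. For 3 kg with SD 5 kg the results are 41.7% and 39.6%, below the stated figure. The t values are used below.

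**2. State at measurement, between groups.** If every reading on a fasting day were fasted and every reading on other days fed, the false difference would be (difference in fasting days / 7) × gap. This is an upper bound when both groups measure at similar times.

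| Difference in fasting days | Weight, gap 0.5-1.5 kg | BP, shift 1-5 mmHg |
|---|---|---|
| 1 per week | 0.07-0.21 kg | 0.14-0.71 mmHg |
| 3 per week | 0.21-0.64 kg | 0.43-2.14 mmHg |

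The between-arm standard error for weight is 5 × √(2/17) = 1.7 kg, so 0.07-0.21 kg is about 4-12% of one standard error.

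A less extreme case assumes 8 hours' sleep, a usual 12-hour overnight fast and readings at random waking times. The fasted share of waking time is then 4/16 on ordinary days and 8/16 on 16-hour fasting days, a difference of one quarter. The 1 day/week figure falls to 0.02-0.05 kg.

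**3. State at measurement, within an arm.** Nothing cancels here. If the baseline is fed and a later reading fasted, the change carries the full gap of 0.5-1.5 kg.

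**4. Precision for systolic BP.** With m readings averaged at both ends, SD² = 225 − 2 × s² × (1 − 1/m), where s is the SD of a single reading. With m = 3 and independent readings:

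| s (mmHg) | SD of change | Power for 10 mmHg |
|---|---|---|
| one reading each end | 15.0 | 47% |
| 4 | 14.3 | 51% |
| 6 | 13.3 | 57% |
| 8 | 11.8 | 67% |
| 10 | 9.6 | 84% |

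Readings in one session share that day's deviation, and averaging does not reduce it. Take s = 8, so s² = 64:

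- Half day-to-day: SD = √(225 − 2 × 32 × 2/3) = 13.5, power 55%.
- Three quarters day-to-day: SD = √(225 − 2 × 16 × 2/3) = 14.3, power 51%.

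**5. Precision for weight.** The same formula with s of 0.5, 1.0 and 1.5 kg gives SDs of 4.97, 4.86 and 4.69 kg and power of 40%, 41% and 44%, against 39.6%. Replicates add little; for weight the case rests on standard conditions.

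**The case against.** The strongest reply is that the plan is silent rather than wrong, and that randomisation covers most of the problem. Several parts of it stand.

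- A reader might infer that each time point rests on one reading taken at any hour. One reading is the natural sense of the prompts, but the number and timing are unstated. The defect is the silence.
- A reader might infer that a lone week-12 or week-18 value is the endpoint. Readings are weekly and section 5.3 uses mixed models, which could draw on all of them. The plan does not say that they will, but the worst case cannot be assumed. Only the baseline is clearly prompted once.
- A reader might infer a material bias towards the commitment arm. Both arms are told to fast and get the same weekly request, so a common shift cancels. The remainder is small against a standard error of 1.7 kg, and the documents give no direction for an acute effect on BP.
- It is tempting to set the artefact against a true effect of 3/7 = 0.43 kg per fasting day, scaling the roughly 3 kg in section 1.2. That section states neither full adherence nor a linear relation, so the comparison is not supported.

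Three things survive the reply. Cancellation does not help within-arm change. It does not help the exploratory comparison, where fasting days differ by construction. It is incomplete between arms if fixed fast times and reminders in one arm alter when people measure, and nothing recorded would show that.

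**Conclusion.** The point holds as a gap in measurement procedure for secondary and exploratory outcomes. The plan sets no conditions for readings that its own regimen can shift, and it takes the baseline before the instruction to fast.

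For the randomised contrast the effect is probably small: at most about one seventh of the fed-fasted shift per 1 day/week difference in adherence. This bound fails if the arms also differ in when they measure. The concern is greater for the exploratory comparison by fasting days and greatest for within-arm change. All these sizes rest on the assumed gaps.

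The precision argument is real for systolic BP but uncertain in size. A reader might take the 67% at a reading SD of 8 mmHg as the expected power. It requires independent readings, which three in one sitting are not, and the documents give no within-person SD.

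The primary adherence outcome is untouched. The change is worth making before enrolment because conditions at measurement cannot be recovered afterwards.

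**What to change.** In sections 4.3 and 4.4, use one measurement script for both arms, at baseline and every week, with the prompt sent in the morning:

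- Weight on waking, before any food or drink.
- BP at the same session, seated and rested, with three readings texted and averaged.
- Baseline BP preferably repeated on more than one day before randomisation, since same-session replicates leave day-to-day variance in place.
- Time since last meal reported with each reading, so that remaining differences in state can be examined.

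In section 5.3, state which weekly values enter the mixed models and that the averages serve as the baseline, week-12 and week-18 values.

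The cuff, scale and text platform are already supplied. The cost is edited message text, a few extra minutes a week for participants, a slightly longer run-in if baseline is repeated, and possibly a few more skipped readings.
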